10.3 Planned Analyses

10.3.1 Interim Analyses

An interim analysis to evaluate the study objectives of correlation between the biomarker (ie baseline intratumoral CD8+ cell density changes in intratumoral CD8+ cell density and other biomarkers) and ORR will be conducted on approximately the first 50 subjects only who received at least 1 dose of talimogene laherparepvec, with the biomarker recorded at baseline, and have had the opportunity to be on study (treatment or follow-up phase) for at least 6 months. The study will not be discontinued due to the results of this interim analyses; however, predictive hypotheses generated from the interim analysis may lead to subsequent changes to study conduct. For example, if the interim analysis suggests an enhanced effect in a biomarker-defined subgroup, then the protocol and statistical analysis plan may be revised to ensure the study can adequately evaluate the subgroup effect. Revisions may also happen due to obtaining new relevant data from external sources, such as scientific publications and communications.

10.3.2 Primary Analysis

The clinical study report (CSR) will be written based on the results of the primary analysis. The main goals of the primary analysis are to evaluate the ORR and correlation of baseline intratumoral CD8+ cell density and the likelihood of response to talimogene laherparepvec, in addition to the correlation between changes in intratumoral CD8+ cell density during treatment and objective response. The timing of the primary analysis will be when all subjects have had the opportunity to complete 12 months of treatment of talimogene laherparepvec.

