The main goals of the primary analysis are to evaluate the correlation between baseline intratumoral CD8+ cell density and ORR, DRR, DOR, and changes in tumor burden, in addition to the correlation between changes in **intratumoral** CD8+ cell density during treatment and ORR, DRR, DOR, and changes in tumor burden. The timing of the primary analysis will be when all subjects have had the opportunity to complete 12 months of treatment with talimogene laherparepvec.

An interim analysis to evaluate the study objectives will be conducted on approximately the first 50 subjects who received at least 1 dose of talimogene laherparepvec, with the biomarker recorded at baseline, and have had the opportunity to be in the study (treatment or follow-up) for 6 months.

The final analysis will occur **either 24 months after the last subject has been enrolled or** when the last subject discontinues the study treatment and has had the opportunity to complete the **safety follow-up, whichever is later.**

Descriptive statistics will be provided for demographic, safety, efficacy, and biomarkers as appropriate. In general, the safety analysis set will be used for all safety analyses. The safety analyses include incidence of treatment-emergent and treatment-related adverse events (all adverse events, \geq grade 3 adverse events, serious adverse events, fatal adverse events and adverse events defined as events of interest).

The efficacy analysis will be conducted using the safety analysis set as well, unless otherwise specified. The ORR will be estimated with the associated 95% CI. Descriptive statistics for DRR, time to treatment failure, changes in tumor burden, and OS will be provided. In addition, DOR and changes in tumor burden for responders will also be summarized.

The correlation between a baseline biomarker and response rate will be evaluated. The functional manner in which the response rate may vary with the biomarker is unknown; therefore multiple functional relationships may be examined. Pearson's correlation coefficient (r) will be estimated between the biomarker change and the maximum decrease in index lesions to evaluate the correlation between changes in a biomarker post-treatment and the effect of treatment on measurable lesions, in addition to correlating biomarker changes with objective response using logistic regression.

[figure not shown]
For further details on the statistical analysis, please refer to [Section 10](#).

Sponsor: Amgen Inc.

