In the open-label, randomized, phase 3 study of talimogene laherparepvec versus subcutaneously administered GM-CSF in stages IIIB, IIIC, and IV unresectable melanoma, talimogene laherparepvec or GM-CSF was administered until CR, clinically significant disease progression, intolerable side effects, 12 months of therapy without an objective response, or withdrawal of consent (Study 20110263; OPTiM). The primary endpoint of the study is durable response rate, defined as the rate of subjects with an objective response by central review (CR or partial response [PR]) lasting continuously for 6 months and starting any time within 12 months of initiating therapy.

Primary analysis of the OPTiM Study showed a statistically significant difference between the rate of durable response among subjects treated with talimogene laherparepvec (16%; 95% CI: 12%, 21%) versus those treated with GM-CSF (2%; 95% CI: 0%, 5%) (p -value < 0.0001). **Overall response rate was also improved from 6% with GM-CSF to 26% with talimogene laherparepvec ($P < 0.0001$, descriptive). Similarly, 11% of patients had a CR in the talimogene laherparepvec arm vs. < 1% in the GM-CSF arm. In the event-driven primary OS analysis (secondary endpoint), median OS with talimogene laherparepvec treatment was 23.3 months compared with 18.9 months with GM-CSF treatment (HR, 0.79 [95% CI, 0.62–1.00]; $P = 0.051$) (Andtbacka et al, 2015). At the final planned analysis of OS which happened when last enrolled subject completed 3 years of follow-up, median OS was 23.3 months in the talimogene laherparepvec arm and 18.9 months in the GM-CSF arm (HR, 0.79; 95% CI, 0.62–1.00; $P=0.049$), (descriptive) (Andtbacka et al, 2015).**

The most common side effects were fatigue, chills, and pyrexia. Serious adverse events occurred in 36% of the talimogene laherparepvec subjects and 21% of the GM-CSF subjects. **The only grade 3/4 adverse event occurring in $\geq 2\%$ of patients was cellulitis (talimogene laherparepvec, $n=6$ [2.1%]; GM-CSF, $n=1$ [$< 1\%$]). Of 10 fatal events in the talimogene laherparepvec arm, none were considered treatment-related per investigator and most (80%) were associated with disease progression with the exception of sepsis in the setting of salmonella infection and myocardial infarction (Andtbacka et al, 2015).**

Refer to the **latest version of the Talimogene Laherparepvec Investigator's Brochure**, for additional information.

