3.5 Estimated Study Duration

3.5.1 Study Duration for Subjects

The subject enrollment period is planned for approximately 17 months.

The duration of the screening period for each subject will be up to 28 days. The duration of treatment will vary for each subject. Subjects will be treated with talimogene laherparepvec until the subject has achieved a CR, all injectable tumors have disappeared, clinically relevant (resulting in clinical deterioration or requiring change in therapy) disease progression beyond 6 months of treatment, per modified WHO response criteria ([Appendix D](#)), or intolerance of study treatment, whichever occurs first. Subjects will be followed for safety 30 (+ 7) days after the last dose of talimogene laherparepvec and for survival, **adverse events thought by the investigator to be potentially related to talimogene laherparepvec, and use of anti-cancer therapy for melanoma** every 12 weeks (\pm 28 days) for up to approximately 24 months after the last subject is enrolled **in the study**. The estimated average per-subject study duration is approximately 32 months.

After the end of the long term follow up subjects who end the study for any reason other than death or withdrawal of full consent will continue to be followed for survival under an ongoing separate registry protocol (Study 20120139). The registry protocol will also monitor for adverse events thought by the investigator to be potentially related to talimogene laherparepvec and use of anti-cancer therapies for melanoma.

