Appendix A. Conventions for Clinical Data That Require Imputation for Partial or Missing Date.....	23
Appendix B. Wilson's Score Method with Continuity Correction in Calculating the 95% Confidence Intervals for Difference in 2 Independent Proportions	25

Table of Abbreviations

Abbreviation/Acronym	Definition
AE	Adverse event
CI	Confidence interval
CR	Complete response
CRF	Case report form
CT	Computerized Tomography
CTC	Common Toxicity Criteria
CTCAE	Common Toxicity Criteria for Adverse Events
DMP	Data management plan
DOR	Duration of Response
DRR	Durable Response Rate
DTP	Data transfer plan
ECOG	Eastern Cooperative Oncology Group
eCRF	Electronic Case Report Form
EOI	Event of Interest
HR	Hazard ratio
HSV	Herpes simplex virus
HSV-1	Herpes simplex virus type 1
IP	Investigational product
IPD	Important protocol deviation
IVRS	Interactive Voice Response System
KM	Kaplan-Meier
MedDRA	Medical Dictionary for Regulatory Activities
ND	Not done
NPV	negative predictive value
OR	Objective response (CR or PR)
ORR	Objective response rate
PD	Progressive disease
PFU	Plaque-forming unit
PPV	positive predictive value
PR	Partial response
PT	Preferred term
qPCR	Real-time polymerase chain reaction
SAE	Serious adverse event
SAP	Statistical analysis plan

Abbreviation/Acronym	Definition
SD	Stable disease
SMQ	Standardized MedDRA Queries
SOC	System organ class
SOP	Standard Operating Procedure
TTF	time to treatment failure
UE	Unevaluable for tumor response
ULN	Upper limit of normal
WHO	World Health Organization
WHODRUG	World Health Organization Drug Dictionary

1. Introduction

The purpose of this statistical analysis plan (SAP) is to provide details of the statistical analyses that have been outlined within the protocol 20120325 entitled “A Phase 2, Multicenter, Open-label, Single-arm Trial to Evaluate the Correlation Between Objective Response Rate and Baseline Intratumoral CD8+ Cell Density in Subjects With Unresected Stage IIIB to IVM1c Melanoma Treated with Talimogene Laherparepvec”.

The scope of this plan includes the primary analysis that is planned and will be executed by the Biostatistics department at Amgen unless otherwise specified. A separate SSAP will be prepared for the exploratory objectives and these analysis may be reported separately.

2. Objectives

Primary Objective:

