11.3 Efficacy Endpoints

The efficacy analysis will be conducted using the safety analysis set unless otherwise specified. The ORR/ DRR/ Disease control rate will be estimated with the associated exact 95% CI ([Clopper and Pearson, 1934](#)). Wilson's score method with continuity correction ([Newcombe, 1998](#)) will be used to calculate an approximation of the exact CI for between-group differences in binary rates. Kaplan-Meier (K-M) estimates of landmarks (e.g., 1-, 2-, and 3-year rates) and quartiles for DOR, time to treatment failure and OS will be provided ([Kaplan and Meier, 1958](#)) . Greenwood's formula ([Kalbfleisch and Prentice, 1980](#)) for standard error will be used to calculate CIs for landmark K-M rates. CIs for K-M quartiles will be estimated ([Brookmeyer and Crowley, 1982](#)). In addition, changes in tumor burden for responders will also be summarized.

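### At the primary analysis DRR is a simple proportion with only 12 months of guaranteed follow-up, so some durable responses may not yet be observable

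*Protocol*

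**What the plan says.** Protocol 10.3.2 sets the primary analysis at the point "when all subjects have had the opportunity to complete 12 months of treatment of talimogene laherparepvec", and the clinical study report is written from it. Section 10.3.2 names ORR and the response correlations as the goals. The synopsis goes further and lists the "correlation between baseline intratumoral CD8+ cell density and ORR, DRR, DOR, and changes in tumor burden" among the main goals.

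The SAP states that "The scope of this plan includes the primary analysis that is planned". Its Section 11.3 says "The ORR/ DRR/ Disease control rate will be estimated with the associated exact 95% CI" and "The efficacy analysis will be conducted using the safety analysis set unless otherwise specified". No minimum follow-up for DRR is visible, nor any rule for a response still ongoing at less than 6 months.

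Protocol 10.1.1.2 lists DRR without defining it. The only definition in view is the phase 3 study's in Protocol 2.2: a response "lasting continuously for 6 months and starting any time within 12 months of initiating therapy". Parts of the SAP's definitions and methods are blacked out, so this trial's own definition may exist there.

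Protocol 3.5.1 adds: "The subject enrollment period is planned for approximately 17 months". Protocol 10.3.3 places a final analysis no earlier than 24 months after last enrolment and says the study report will then be amended.

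**The concern.** A response that may start as late as month 12 and must then last 6 months takes up to 18 months to observe. The cut-off guarantees 12. A binomial proportion over all treated subjects has only two outcomes, so a response that began recently and is still ongoing falls, by default, among the non-durable.

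The error runs in one direction, depends on enrolment date, and is not reflected in the exact interval. Time to treatment failure has an explicit censoring rule, and duration of response and OS are analysed by Kaplan-Meier. DRR depends on duration too but has no comparable handling in the visible text.

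What is at stake is the DRR in the first study report and its relation to CD8+ density. Protocol 10.4.2 contemplates trend tests, comparisons at all cut-points, and predictive values for DRR, with patient selection in view. With fewer than 20 durable responders expected, reclassifying one to three can move such results.

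**Working it through.** **The plan's own figures.** None is given for DRR. The exact-interval method can be checked on Protocol Table 4: at N = 110 it gives 13.0% to 28.7%, 21.6% to 39.5%, 30.8% to 49.8% and 40.3% to 59.7%, matching the table. The stated 88% power concerns ORR and also reproduces (88.4%).

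**Inputs from the documents**
- Minimum potential follow-up at the cut-off: 12 months (Protocol 10.3.2).
- Enrolment period: 17 months (Protocol 3.5.1).
- Tumour assessments: every 12 weeks (Protocol Table 2).
- DRR of 16% in the phase 3 study (Protocol 2.2), used as an illustrative true value: 110 × 0.16 = 17.6 durable responders.

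**Assumptions**
- The phase 3 definition applies.
- Accrual is even, so potential follow-up at the cut-off is uniform from 12 to 12 + 17 = 29 months.
- Onset is first seen at weeks 12/24/36/48 in shares from 60/25/10/5 to 30/35/20/15. The documents say only that fewer than 5% of responders had onset after 12 months (Protocol 10.2).
- Durability is shown at the first scheduled visit at least 24 weeks, or at least 183 days, after onset.

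**Share not yet observable.** If durability is first shown at month v, the share of subjects with too little follow-up is max(0, (v − 12)/17), with 4.348 weeks per month.

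| Onset | 24 weeks: shown at | Missed | 183 days: shown at | Missed |
|---|---|---|---|---|
| wk 12 | wk 36 = 8.3 mo | 0 | wk 48 = 11.0 mo | 0 |
| wk 24 | wk 48 = 11.0 mo | 0 | wk 60 = 13.8 mo | 0.106 |
| wk 36 | wk 60 = 13.8 mo | 0.106 | wk 72 = 16.6 mo | 0.268 |
| wk 48 | wk 72 = 16.6 mo | 0.268 | wk 84 = 19.3 mo | 0.430 |

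**Weighted by onset share**
- 24 weeks, early onset: 0.10 × 0.106 + 0.05 × 0.268 = 2.4%.
- 24 weeks, later onset: 0.20 × 0.106 + 0.15 × 0.268 = 6.1%.
- 183 days, early onset: 0.25 × 0.106 + 0.10 × 0.268 + 0.05 × 0.430 = 7.5%.
- 183 days, later onset: 0.35 × 0.106 + 0.20 × 0.268 + 0.15 × 0.430 = 15.5%.

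**Effect on a true DRR of 16%**, as 16% × (1 − share missed)
- 24 weeks: 15.6% to 15.0%, or 0.4 to 1.1 of 17.6 responders.
- 183 days: 14.8% to 13.5%, or 1.3 to 2.7 of 17.6.

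**Sensitivity to onset.** Exponential onset with 5% after month 12 gives 3.2% (24 weeks) or 9.3% (183 days). Equal shares at the four visits give 9.3% or 20%. If every onset is at week 12, the loss is zero under either reading. If every onset is at week 48, it is 27% or 43%.

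**Final analysis.** Minimum follow-up is at least 24 months, beyond the latest figure of 19.3 months, so the loss is 0%.

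**The case against.** The strongest reply is that the plan already contains the remedy. The final analysis comes at least 24 months after last enrolment, the report is amended then, and Protocol 7.2.4 continues tumour assessments in subjects who stop treatment for reasons other than progression or death. Duration of response is also summarised by Kaplan-Meier at the primary analysis, so a follow-up-adjusted view of durability exists. All this stands. It confines the problem to the primary-analysis DRR, but does not tell readers of the first report that this figure is immature.

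The shift is also small against sampling error: 18 of 110 has an exact 95% interval of 10.0% to 24.6%, and the largest main-scenario shift (16% to 13.5%) lies well inside it. That stands too. Analyses are descriptive and DRR is secondary.

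A reader might infer several stronger things that the documents do not support:
- **That the SAP instructs ongoing short responses to be scored as failures.** No visible text says so. It is the default consequence of a proportion over all treated subjects, and a rule may lie in redacted text.
- **That this trial requires an 18-month window.** That definition belongs to the phase 3 study.
- **That all late enrolees are affected.** About 6/17 = 35% of subjects have under 18 months of potential follow-up, but misclassification also needs a later onset.
- **That the primary endpoint is compromised.** It uses ORR, and fewer than 5% of responders are expected to have onset after 12 months.

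**Conclusion.** The point holds in a limited form. With the visible estimator at the stated cut-off, and under the phase 3 definition, the primary-analysis DRR is biased low. In the main scenarios the loss is about 2% to 6% of durable responders if 24 weeks counts as 6 months, and 8% to 16% if 183 days is required: roughly 0.4 to 2.7 subjects. It disappears at the final analysis.

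The direction is firm if 6 months' duration is required and some responses begin late enough. The size rests on assumed onset shares, even accrual and scheduled visits only; extra assessments, which the protocol allows when clinically indicated, could alter it. The effect on the CD8+ correlations has not been quantified, and their methods are partly redacted. This is a worthwhile, inexpensive clarification, not a defect in the trial's main result.

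**What to change.** In the SAP:

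1. State this trial's DRR definition, including whether 24 weeks or 183 days is 6 months, if the unredacted text does not already do so.
2. Name the planned final analysis as definitive for DRR and its CD8+ correlations, and extend the SAP's stated scope to match.
3. At the primary analysis, label DRR immature and report ongoing responses under 6 months separately, not as failures.
4. Add a censoring-aware estimate: ORR times the Kaplan-Meier probability that response lasts at least 6 months. It assumes duration is unrelated to available follow-up. Later responders have less follow-up, so this should be stated.

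If a follow-up restriction is preferred to item 4, set it at the first scheduled visit that can verify a week-48 onset: about 19.3 months for 183 days, or 16.6 months for 24 weeks. An 18-month rule does not fit the 183-day reading: (19.3 − 18)/(29 − 18) = 12% of the retained subjects would still be too early for that onset.

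Cost: SAP wording, with no new visits or subjects. The definitive DRR arrives later. A restricted primary estimate would use only (29 − 19.3)/17 = 57% to (29 − 16.6)/17 = 73% of subjects, about 63 to 80 of 110, and would be less precise.

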10.3.3 Final Analysis

The final analysis will occur **either 24 months after the last subject has been enrolled or** when the last subject discontinues the study treatment and has had the opportunity to complete the **safety follow-up, whichever is later**. The CSR will be amended with the updated results from the final analysis at the completion of the study.

10.4 Planned Methods of Analysis

Descriptive statistics will be provided for demographic, safety, efficacy, and biomarkers as appropriate. In general, the safety analysis set will be used for all safety analyses. The safety analyses include incidence of treatment-emergent and treatment related adverse events (all adverse events, \geq grade 3 adverse events, serious adverse events, fatal adverse events and adverse events defined as events of interest).

The efficacy analysis will be conducted using the safety analysis set as well unless otherwise specified. The ORR will be estimated with the associated 95% CI.

Descriptive statistics for DRR, time to treatment failure and OS will be provided. In addition, DOR and changes in tumor burden for responders will also be summarized.

The correlation between a baseline biomarker and response rate will be evaluated. The functional manner in which the response rate may vary with the biomarker is unknown; therefore multiple functional relationships may be examined. Pearson's correlation coefficient (r) will be estimated between the biomarker change and the maximum decrease in index lesions to evaluate the correlation between changes in a biomarker post-treatment and the effect of treatment on measurable lesions, in addition to correlating biomarker changes with objective response using logistic regression.

10.4.1 Primary Endpoint

The primary endpoint of the study is the correlation between baseline intratumoral CD8+ cell density and objective response rate (ORR). The correlation of intratumoral

CD8+ cell density and other biomarkers with ORR will be evaluated as described in [Section 10.4](#) for ORR and DRR.

10.4.2 Secondary Endpoint (s)

Multiple biomarkers will be examined to assess the correlation between their baseline value and DRR, DOR, and changes in tumor burden as well as the changes in their value during treatment with ORR, DRR, DOR, and changes in tumor burden. The functional manner in which the ORR, DRR, DOR, and change in tumor burden may vary with each biomarker is unknown, therefore multiple functional relationships will be examined to assess overall evidence of an association. Combinations of biomarkers may be explored to assess their predictive value for patient selection. Example analyses include, but are not limited to: (a) the correlation of baseline value as a continuous variable with the odds of OR, DR or the hazard of ending response; (b) a trend test for an increasing ORR, DRR with pre-specified, ordered biomarker categories, (c) a test that the ORR, DRR or hazard of ending response is greater between subgroups of subjects with a high vs. low baseline biomarker value for all possible cut-points for a minimum high biomarker value, (d) a receiver operating characteristic (ROC) analysis (categorical and continuous biomarker values), and (e) calculation of negative predictive value (NPV) and positive predictive value (PPV) for each candidate cut-point for ORR and DRR.

In order to evaluate the correlation between changes in biomarkers during treatment and the effect of treatment on measurable lesions, Pearson's correlation coefficient (r) will be estimated between the biomarker change and the maximum decrease in index lesions, in addition to correlating biomarker changes with ORR/DRR using logistic regression, and duration of response using Cox model regression.

Overall survival (OS), duration of response and time to treatment failure will be summarized by K-M methods. Durable response rate and objective response rate will be presented with 95% CI.

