2.3 Rationale

The purpose of the study is to explore the correlation between baseline intratumoral CD8+ cell density and objective response rate (ORR) in subjects with unresected stage IIIB to IVM1c melanoma. In addition, the study is planned to inform on the mechanism (s) of systemic action of talimogene laherparepvec on distant metastatic tumors and to identify candidate biomarkers which may predict treatment outcome. Biopsy samples will be used to investigate the relationship between intratumoral CD8+ cell density and response to treatment. Leaving one lesion uninjected during the treatment for biopsy at week 6 is critical for defining the proposed locally-initiated systemic anti-tumor immune response of talimogene laherparepvec. One hypothesis is that tumors with significant number of infiltrating CD8+ T cells will be more likely to respond to an immunotherapy with talimogene laherparepvec. Additionally, we hypothesize that talimogene laherparepvec treatment increases the number of tumor antigen specific T cells and further that subjects with higher levels of tumor antigen specific T cells will have greater response to treatment. In addition to examining the association, if any, between tumor infiltrating T cells prior to treatment and clinical response to treatment, a number of other biomarkers will be assessed to determine any association with response. CCI [REDACTED]

[REDACTED]

[REDACTED]

[REDACTED]

[REDACTED]

[REDACTED]

[REDACTED]

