10.2 Sample Size Considerations

All analyses will be descriptive with no formal hypothesis testing. The sample size was selected based on practical considerations. The primary objective of the study is to assess whether baseline intratumoral CD8+ cell density is correlated with the likelihood of response to talimogene laherparepvec. Analyses for the objective will focus on whether the response rate varies with baseline intratumoral CD8+ cell density. The functional manner in which the response rate may vary with the biomarker is unknown, therefore multiple functional relationships may be examined. It is assumed that 100 subjects (approximately 91% of the enrolled) will have an evaluable baseline intratumoral CD8+ cell density. The adequacy of the sample size was evaluated for one of several possible analyses that evaluates whether the response rate is positively correlated with a high baseline intratumoral CD8+ cell density where a low and high biomarker is defined as a value below versus at or above the sample median, respectively. A one-sided Fisher's Exact test will be performed at a 5% nominal level to explore the hypothesis that the response rate is equal regardless of baseline intratumoral CD8+ cell density. The overall ORR is assumed to be 26.4%. The power for the test will depend on the true response rates in the biomarker subgroups. Assuming the true response rate is 13.2% in the biomarker low subgroup, and 39.6% in the biomarker high subgroup, the power will be 88% to detect a positive association.

A secondary objective of this study is to estimate the objective response rate. Based on the analysis of the OPTiM study, the overall response rate for stage IIIB/C and IVM1c is assumed to be around 26.4% where, among responders, the probability of response onset after 12 months was < 5%. The expected exact 95% CIs for various true ORRs are listed in [Table 4](#). The expected width of the 95% CI is around 18% under these scenarios.

Table 4. Expected 95% Confidence Intervals by Various True ORRs

Subjects enrolled (N)	True	Expected 95% CI (width)
110	20%	13% - 29% (16%)
	30%	22% - 39% (18%)
	40%	31% - 50% (19%)
	50%	40% - 60% (19%)

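### Protocol 10.4.2 item (c) uses one direction, greater in biomarker-high subjects, for ORR, DRR and the hazard of ending response; for the hazard that is the unfavourable direction

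*Protocol*

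**What the plan says.** Protocol 10.1.1.2 makes the correlation of baseline CD8+ density with duration of response (DOR) a secondary endpoint. Protocol 10.4.2 describes how such correlations may be examined, for several biomarkers. It opens its list with "Example analyses include, but are not limited to". The entries that matter here are:

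- Item (a): "the correlation of baseline value as a continuous variable with the odds of OR, DR or the hazard of ending response". No direction is stated.
- Item (c): "a test that the ORR, DRR or hazard of ending response is greater between subgroups of subjects with a high vs. low" value of a biomarker at baseline, over all possible cut-points. No test, level or sidedness is named.

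The same section plans to analyse "duration of response using Cox model regression" against biomarker changes, and to summarise DOR by Kaplan-Meier methods.

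The expected direction for CD8 appears in two places, both about response rather than its duration. Protocol 2.3 says "One hypothesis is that tumors with significant number of infiltrating CD8+ T cells will be more likely to respond". Protocol 10.2 sizes the study on an analysis of "whether the response rate is positively correlated with a high baseline intratumoral CD8+ cell density", using a one-sided Fisher's exact test at a nominal 5%.

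**The concern.** In item (c) the word for the direction is shared by quantities that run opposite ways. Higher ORR and DRR in the high group are good outcomes. A higher hazard of ending response in the high group means those subjects lose their responses sooner. Programmed as worded, the DOR comparison would put its rejection region in the unfavourable tail while the two comparisons next to it use the favourable one.

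Two misreadings could follow. A real lengthening of response in CD8-high subjects would give a large p-value from this test. A small p-value would mean faster loss of response, yet it would stand beside ORR and DRR p-values whose small values mean benefit. Describing the p-values as descriptive does not remove the problem. SAP 11.1 wants them to indicate comparative strength of association, and a p-value from the wrong tail does that badly.

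Of the listed examples, only (a) and (c) name the hazard of ending response, and (c) is the one that compares high with low groups. The SAP (11.1) counts cut-off values for patient selection among its main goals.

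**Working it through.** **The plan's own figure.** Protocol 10.2 states 88% power for the ORR comparison. Inputs: 100 evaluable subjects, taken as 50 low and 50 high by the median split; response rates 13.2% and 39.6%; one-sided Fisher's exact test at 5%. Exact enumeration over the two binomials gives 88.4%. The figure reproduces, and this point does not touch it. The documents give no power, event count or hazard ratio for DOR.

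**Inputs for the hazard comparison.**

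- Responders: 50 × 0.396 + 50 × 0.132 = 19.8 + 6.6 = 26.4, so about 26 (from 10.2).
- Share of responders who are CD8-high: 19.8 / 26.4 = 0.75. This holds for the median split only; 0.5 is shown as an alternative. Events are assumed to divide in the same proportion.
- Events *d* (ends of response): assumed, 10 to 20 of the 26 responders.
- Hazard ratio, high versus low: assumed, 0.5 or 0.33.
- Level: one-sided 5%, borrowed from the ORR test in 10.2. Item (c) does not state it.

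**Formula** (Schoenfeld approximation). With high share *a*, let s = √(d·a·(1−a)) × |ln HR|.

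- Hazard lower in the high group (favourable): power = Φ(s − 1.645).
- Hazard greater in the high group (as worded): power = Φ(−s − 1.645).

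**Worked case**, d = 15, a = 0.75, HR = 0.5: s = √(15 × 0.1875) × 0.693 = 1.677 × 0.693 = 1.162.

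- Favourable: Φ(−0.482) = 31%.
- As worded: Φ(−2.807) = 0.25%.
- At the expected z of 1.16, the one-sided p-value is about 0.12 in the favourable tail and 0.88 as worded.

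**Range.**

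| Events | CD8-high share | HR | Favourable tail | As worded |
|---|---|---|---|---|
| 10 | 0.75 | 0.5 | 24% | 0.47% |
| 15 | 0.75 | 0.5 | 31% | 0.25% |
| 15 | 0.75 | 0.33 | 58% | 0.02% |
| 20 | 0.5 | 0.5 | 46% | 0.07% |
| 20 | 0.5 | 0.33 | 80% | 0.002% |

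A two-sided 5% test in the worked case has 21% power.

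The qualitative result needs none of these assumptions except the one-sided reading. For any hazard ratio below 1, s is positive, so the test as worded rejects less often than its nominal 5%.

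**The case against.** A reader might infer that longer response in CD8-high subjects could not be detected in this study. The documents do not support that. Item (c) is one example in an open-ended list, and 10.4.2 says "multiple functional relationships will be examined to assess overall evidence of an association". Item (a) relates continuous baseline value to the same hazard with no direction attached. Kaplan-Meier summaries, if shown by CD8 group, would reveal which way the curves separate. (The Cox regression is less help here, because it concerns biomarker change rather than baseline value.) This part of the objection stands, so the point is confined to test (c).

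Second, (c) names no sidedness. Its phrasing is loose enough that the authors may have meant only a comparison between groups. That also stands, and it makes every power figure above conditional. It does not rescue the sentence: if a two-sided comparison was intended, the directional wording is still wrong.

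Third, 2.3 and 10.2 concern the likelihood of response, and 10.4.2 covers several biomarkers. A favourable direction for DOR with CD8 is therefore a reasonable inference, not a stated hypothesis. This limits how far (c) can be said to contradict the study's hypothesis. The inconsistency with ORR and DRR inside the same clause remains for any biomarker.

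Fourth, nothing can be drawn from the SAP's silence. Its CD8-versus-response methods in 11.4 are largely redacted and may already handle the direction.

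Finally, all analyses are descriptive, and the documents do not say how a large or small p-value from (c) would be reported. The misreadings described are risks, not planned conclusions.

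**Conclusion.** The point holds as a wording error in one listed secondary analysis. Item (c) gives ORR, DRR and the hazard of ending response the same direction, and for the hazard that direction is unfavourable. Taken literally as a one-sided 5% test, (c) would show longer response in CD8-high subjects with probability below 0.5% across 10 to 20 events, 50% to 75% CD8-high and hazard ratios of 0.5 and 0.33. The favourable tail would give 24% to 80%. Events, hazard ratios and the one-sided level are assumptions, and the 75% share rests on the median-split response rates. Even in the favourable tail, about 26 responders give limited power for DOR.

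The primary endpoint, the 88% power statement, the sample size and data collection are unaffected. Severity is minor.

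**What to change.** Reword item (c) as a test that ORR or DRR is greater, or that the hazard of ending response is lower (longer DOR), in subjects with a high rather than a low baseline biomarker value. Alternatively, make the DOR comparison two-sided and report the hazard ratio with its 95% CI. The second option avoids assuming a direction for biomarkers other than CD8. In either case state the sidedness and nominal level for each measure in (c), and align any matching text in SAP 11.4.

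The cost is one sentence in Protocol 10.4.2 and a check of the SAP. There is no effect on data collection or sample size.
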